Feasibility is to be measured using a 10-question phone survey 1 week following the dosage (see appendix A - attached). Efficacy will be measured by the 25OHD level itself; if 25OHD levels are found to be between 30-100 ng/mL over the course of the study, the dose will have demonstrated effectiveness in achieving the study's goal.

The purpose of this study is to show that 25OHD levels can be safely corrected with a one-time dose of vitamin D3 and be feasibly provided in the outpatient setting to children with CF.

2. Objectives (include all primary and secondary objectives)

Primary

1. Assess the safety of a single dose of oral vitamin D3 (250,000 IU) for the treatment of vitamin D insufficiency in pediatric cystic fibrosis patients.

Date: December 20, 2016

Principal Investigator: [name]

Application Number: IRB00081746 (IND # 128487 – IND Sponsor: [name])

Secondary

1. Assess the feasibility of undertaking a future large scale randomized controlled trial. Specifically, we will:
 - (a) Assess the acceptability and timing of the selected outcome measures;
 - (b) Obtain estimates needed to design a full-scale randomized trial design (if warranted), including: number of eligible participants, recruitment rate, retention rate, response rates to initial and follow up questionnaires.
2. Determine the efficacy of a single dose of oral vitamin D3 (250,000 IU) for the treatment of vitamin D insufficiency in pediatric cystic fibrosis

3. Background

Cystic Fibrosis is an inherited disease that primarily affects the lungs but also can affect the pancreas, liver and gastrointestinal tract. Subsequently, the bone health of individuals is also compromised due to complications arising from malnutrition, malabsorption, and repeated pulmonary exacerbations.

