Vitamin D toxicity or hypervitaminosis D is characterized by elevated serum calcium levels or hypercalcemia (14). Due to the hypercalcemia, acute symptoms of toxicity can include muscle weakness, confusion, vomiting, anorexia, polyuria and polydipsia. In addition, hypercalcemia can be chronic, and those symptoms of intoxication from hypervitaminosis D could include bone demineralization, pain, and nephrocalcinosis.

Therefore, we believe STOSS therapy will efficaciously, safely and feasibly increase vitamin D levels to above 30 ng/mL in our pediatric CF population. We hypothesize that STOSS therapy

Date: December 20, 2016

Principal Investigator: [name]

Application Number: IRB00081746 (IND # 128487 – IND Sponsor: [name])

administered once in clinic as witnessed by a designated clinician, will maintain 25OHD levels greater than or equal to 30 ng/mL without instances of hypercalcemia (7).

4. Study Procedures

The study is a phase 2 single arm study that will assess the safety, feasibility and efficacy of a high dose of vitamin D3 as cholecalciferol in Cystic Fibrosis pediatric patients with a 25OHD level <30 ng/mL. The members of the study team will enroll 30 participants who have consented and meet eligibility criteria, including a baseline 25OHD level <30 ng/mL which is measured annually, at a minimum, as a part of the current standard of care. All patients with CF, will be consented to participate upon having his/her annual lab work collected.

As patients present with a 25OHD level < 30 ng/mL they will be screened to see if they meet full eligibility criteria for enrollment. This will include a phosphorus level and spot urine calcium to creatinine ratio which will be collected at their CF visit (patients seen at the St. Petersburg office) or within 2 weeks prior to their visit if in Sarasota or Tampa. (See section 5 for complete inclusion/exclusion criteria). Screening will also consist of a urine pregnancy test to be completed the day of the administration of the high dose of vitamin D.

After a patient meets full eligibility criteria, they will be enrolled in the study and we will administer the 250,000 IU vitamin D3 at that visit. Upon administration, each participant will be provided with an oral, one-time dosage of vitamin D3 (cholecalciferol) in the form of capsules that will be swallowed; the capsule cannot be crushed or dissolved in anything in order to be administered.

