Regardless of serum calcium level or other labs collected, if a participant does become ill after taking the high dose of vitamin D3 (e.g., muscle weakness, confusion, vomiting, anorexia, polyuria and polydipsia, etc.) they will be asked to call the CF office number, [contact]. During this communication, it will be decided if any type of treatment will be needed to remedy the complaint (see section on treatment of hypervitaminosis D from hypercalcemia). If their serum calcium level was within normal limits for age, but they have symptoms of those found with hypercalcemia, it will be noted in our study findings but not classified as an adverse event.

At 12 weeks (± 30 days) from the initial study visit, participants will be required to have another 25OHD level measured via venipuncture as a part of standard of care. In addition, as a part of the

Date: December 20, 2016

Principal Investigator: [name]

Application Number: IRB00081746 (IND # 128487 – IND Sponsor: [name])

first tier of safety measures, a serum calcium and serum phosphorus level will be measured again. If either of these levels is elevated, a PTH level will be measured as soon as possible within approximately 14 days (\pm 3 days) of this serum calcium lab draw. If serum calcium level is above ULN a spot urine calcium to creatinine ratio will be ordered. At 26 weeks (\pm 30 days) and 52 weeks (\pm 30 days) the participants will have 25OHD levels measured again. No additional one-time high dosage of vitamin D3 will be prescribed or provided during the study period for any reason to any of the participants. No additional measures of safety, in the forms of serum calcium labs, serum phosphorus, or PTH will be measured.

Any participant with an elevated serum calcium level of anything above normal limits for age will be instructed to limit calcium containing foods in their diet, stop supplements with additional vitamin D and/or calcium. Since these participants will be called regarding their elevated serum calcium level to query about symptoms of hypercalcemia, we will be able to instruct them on this.

If at any time after the study intervention has started and the participant has a 25OHD level less than 30 ng/mL, they will be placed on the current standard CF Foundation step-wise guidelines for treatment appropriate for their low vitamin D level.

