There will not be a placebo group, as the study design does not support this; providing a placebo is not ethical in this population for this condition.

If a patient does not complete the study for any reason, meaning they do not get each set of lab work completed, their results up to that point in time will still be used in the study but their duration of participation will be noted in the results section. Every effort will be made to contact patients who are lost to follow up to ascertain the reason for withdrawal.

Date: December 20, 2016

Principal Investigator: [name]

Application Number: IRB00081746 (IND # 128487 – IND Sponsor: [name])

| Study Procedures | Study Time-points | | | | | | | |
|---|---------------------------|---------------|---------------------|---|------------------------------|--|---------------------------|------------------------|
| | Screening/ Eligibility | Base- line | Week 1 +/- 3 day | Week 1 B.*** Week 1+/- 14 days | Week 12 +/- 30 days | Week 12 B.*** Week 12 +/- 42 days | Week 26 +/- 30 days | Week 52 +/- 30 days |
| Informed Consent | X | | | | | | | |
| 25OHD Lab | X | | | | X | | X | X |
| Screening / Eligibility Verification (including pregnancy test) | X | | | | | | | |
| Eligibility screening: Spot Urine Calcium to Creatinine Ratio | X | | | | | | | |
| Study Registration | | X | | | | | | |
| Medication Review* | | X | | | X | | X | X |
| STOSS Vitamin D3 Administration | | X | | | | | | |
| Serum Calcium Test & Hypercalcemia Monitoring | | | X | X | X | X | | |
| Serum Phosphorus | X | | X | X | X | X | | |
| Parathyroid Hormone (PTH) Level (2 nd tier only) | | | | X | | X | | |
| Spot Urine Calcium to Creatinine Ratio (2 nd tier only) | | | | X | | X | | |
| Administration of Appendix A Questionnaire | | | X | | | | | |
| Adverse Event Assessment** | | X | X | X | X | X | X | X |

* Medication review will consist of surveying the patient's current daily maintenance dosage for vitamin D as previously prescribed.

** AEs and SAEs are defined per 21CFR312.32. All adverse events will be monitored and processed from study start until 30 days after study product administration. All adverse events deemed related to known vitamin D supplementation risks and/or study procedures will be monitored for 12 months post drug administration.

Date: December 20, 2016

Principal Investigator: [name]

Application Number: IRB00081746 (IND # 128487 – IND Sponsor: [name])

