1. Off-Treatment Criteria: Any patient who requires high dose supplemental vitamin D prescribed outside the study.
2. Off-Study Criteria:
 - a. Refusal of further study follow-up by patient or legal guardian

Date: December 20, 2016

Principal Investigator: [name]

Application Number: IRB00081746 (IND # 128487 – IND Sponsor: [name])

- b. Lost to follow-up
- c. Death
- d. Completion of study requirements

8. Reporting Mechanisms

1. Study Registration

- a. All patients will be registered by the Research Coordinator. The following forms will be completed: Eligibility checklist, On-study form, and Concomitant information form.

2. Toxicity and /or Adverse Reactions

- a. All adverse events will be monitored and processed from study start until 30 days after study product administration.
- b. All adverse events deemed related to known vitamin D supplementation risks and/or study procedures will be monitored for 12 months post drug administration. Serious adverse events will be defined by the criteria specified in 21CFR312.32.
- c. All safety-related event meeting FDA's expedited or annual reporting requirements as stated in 21 CFR 312.32 and 21 CFR 312.33, respectively, will be reported to the FDA.
- d. All safety-related events meeting the IRB's reporting requirements will be submitted to the IRB.

3. Informed Consent

- a. All patients and/or their legal guardian must sign a document of informed consent consistent with local institutional and federal guidelines stating that they are aware of the investigational nature of this protocol and of the possible side effects of treatment. Further, patients must be informed that no efficacy of this therapy is guaranteed and that unforeseen toxicities may occur. Patients have the right to withdraw from this protocol at any time. No patient will be accepted for treatment without such a document signed by him or his legal guardian. Full confidentiality of patients and patient records will be provided according to institutional guidelines.

4. Clinical Trial Oversight and Monitoring

- a. This protocol will be monitored and evaluated in accordance with Johns Hopkins All Children's Hospital CTRO's quality assurance procedures.

9. Statistical Analysis

The primary safety endpoint will be serum calcium levels one-week after administration of the high dose of vitamin D3. Other variables related to safety include the frequency and severity of adverse events and early stopping rules.

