Serious Adverse Experiences (SAE): An SAE is defined as any AE that results in any of the following outcomes:

- Death;

Date: December 20, 2016

Principal Investigator: [name]

Application Number: IRB00081746 (IND # 128487 – IND Sponsor: [name])

- Life-threatening adverse experience;
- In-patient hospitalization or prolongation of existing hospitalization;
- Persistent or significant disability/incapacity;
- Other important medical events may also be considered an SAE when, based on appropriate medical judgment, they jeopardize the participant or require intervention to prevent one of the outcomes listed.

For this study, important medical events that will be reported as an SAE per protocol also include:

If at any time >10% of the participants experience hypercalcemia, accrual will be held pending safety analysis and will be restarted only with the approval of the Data Safety Monitoring Board.

A hypercalcemia level with serum calcium measure of > 13.5 mg/dL requiring hospitalization and treatment.

The following additional demographic and clinical information will be collected at baseline for each participant: Age, gender, pancreatic status (pancreatic insufficiency or pancreatic sufficiency), brand of daily vitamin, prescribed dosage and amount of vitamin D3 in prescribed daily dosage. Qualitative data on the appropriateness of study materials and reasons for nonparticipation and attrition will also be collected to inform future improvement in study materials and recruitment and retention strategies.

Demographic and clinical characteristics of participants will be summarized using counts and percentages for categorical variables and mean and standard deviation or median and range for continuous variables. The mean and corresponding standard deviation of serum calcium level one-week after administration of the high dose of vitamin D3 as well as the proportion and 95% confidence interval of participants with elevated serum calcium levels for age will be calculated.

Feasibility and efficacy parameters including recruitment rate, retention, response percentages to initial and follow up questionnaires and proportion of participants with serum 25OHD level >30 ng/mL at the end of the study will be calculated with the corresponding 95% confidence intervals. All adverse events and study related adverse events will be summarized using counts and percentages.

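### The only named efficacy estimate, the week-52 proportion with 25OHD above 30 ng/mL, has no rule for children given further vitamin D after a low level, and the success criterion differs between sections.

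*Combined protocol and SAP*

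**What the plan says.** The secondary efficacy objective (Section 2) is to "Determine the efficacy of a single dose of oral vitamin D3 (250,000 IU) for the treatment of vitamin D insufficiency". Section 9 gives one statistic for it, with a 95% confidence interval: the "proportion of participants with serum 25OHD level >30 ng/mL at the end of the study will be calculated". The study calendar schedules post-dose 25OHD at weeks 12, 26 and 52, so the end of the study is week 52.

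Section 4 provides that a participant with a level below 30 ng/mL at any time after the intervention has started is treated: "they will be placed on the current standard CF Foundation step-wise guidelines for treatment appropriate for their low vitamin D level". Sections 4 and 10 also tell participants with raised serum calcium to stop supplements containing vitamin D.

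Two nearby rules might be expected to settle the counting:
- Section 7 defines an off-treatment category, "Any patient who requires high dose supplemental vitamin D prescribed outside the study", but attaches no analysis consequence to it. It does not say whether step-wise treatment falls within it.
- Section 4 says of participants who miss lab work that "their results up to that point in time will still be used in the study". That addresses incomplete data, not added treatment.

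Success is described in several ways. Section 1: "if 25OHD levels are found to be between 30-100 ng/mL over the course of the study, the dose will have demonstrated effectiveness". Section 3: the dose "will maintain 25OHD levels greater than or equal to 30 ng/mL without instances of hypercalcemia". Sections 1 and 3 also speak more loosely of raising the level above 30. Section 9 uses above 30 at the end, with no upper limit.

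**The concern.** The protocol expects some children to receive further vitamin D before the only efficacy time point it names, yet has no rule for them. The statistic as written then describes one dose followed by standard care, while the objective and the Section 3 hypothesis are about what the single dose achieves and maintains. A reader who takes the week-52 figure as the answer to Objective 2 would credit the dose with levels reached after added treatment.

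The varying criterion adds a second ambiguity: the same 25OHD record can be a success in one section and a failure in another, so the definition could be settled after the data are seen.

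**Working it through.** There is no stated efficacy rate to reproduce. The inputs are N = 30 (Section 9), the visit schedule and windows (Section 4 calendar) and the treatment trigger (Section 4).

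**Step 1: can the literal reading differ from a sustained response?** The table applies each criterion to example records, reading Section 1 as applying at every visit. The levels are illustrative.

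| Weeks 12 / 26 / 52 (ng/mL) | Section 9 | Section 1 (30-100 throughout) | Section 3 (maintain at least 30) |
|---|---|---|---|
| 35 / 35 / 35 | success | success | success |
| 25, then treated / 35 / 35 | success | failure | failure |
| 35 / 35 / exactly 30 | failure | success | success |
| 35 / 35 / above 100 | success | failure | success on level |

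A child at exactly 30 is neither treated under Section 4 nor counted as a success under Section 9.

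**Step 2: direction.** Let W be the children meeting the threshold at week 52 and S those meeting it at weeks 12, 26 and 52. With one threshold and complete levels, S is a subset of W, so W/30 is at least S/30. The gap is k/30, where k is the number who were low earlier and met the threshold at week 52.

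**Step 3: is there time for added treatment to act?**
- From week 12, nominal: 364 − 84 = 280 days. Shortest within windows: (364 − 30) − (84 + 30) = 220 days.
- From week 26, nominal: 364 − 182 = 182 days. Shortest within windows: (364 − 30) − (182 + 30) = 122 days.

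So treatment can act before week 52. When it would start is not stated.

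**Step 4: size.** Each such child adds 1/30 = 3.3 points. For illustration, assume 12 of 30 sustained the level (exact Clopper-Pearson 95% intervals):

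| k | Reported week-52 proportion | 95% CI |
|---|---|---|
| 0 | 12/30 = 40.0% | 22.7-59.4 |
| 1 | 13/30 = 43.3% | 25.5-62.6 |
| 3 | 15/30 = 50.0% | 31.3-68.7 |

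More generally, if T children are treated after a low level at week 12 or 26, the gap lies between 0 and T/30. For assumed T of 6, 12 or 18 the upper limits are 20, 40 and 60 points, reached only if every treated child is above 30 at week 52. The documents supply neither T nor the share who recover.

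**The case against.** The best defence is that the endpoint is secondary, descriptive and explicitly unpowered, that Section 9's list is open and so does not bar other summaries, and that the needed levels and vitamin D intake are already collected. A sustained proportion could be derived later without new data. The sponsor may also intend one dose followed by standard care, for which the as-measured proportion is the right figure. All of this stands and limits the weight of the point. It does not supply the missing counting rule, and the plan does not say that standard care is part of the target.

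Four stronger readings are tempting but unsupported:
- *The week-52 proportion is biased upwards against any target.* Not shown. Children with raised calcium are told to stop vitamin D supplements, which could lower later levels. The inequality holds only against the observed sustained proportion.
- *Treatment will have run its full course by week 52.* Section 3 reports, anecdotally, that caregivers often have not obtained the vitamin by the visit 2-3 months later. It gives no start date, so the time on treatment cannot be calculated.
- *Sections 1 and 3 uniformly contradict Section 9.* Both also contain above-30 wording that matches Section 9's cut-off; the sections are mixed.
- *A future trial will be mis-sized.* Section 9 speaks of estimating parameters for a later trial, but the estimates listed under the feasibility objective are eligible number, recruitment, retention and questionnaire response. Use of the 25OHD proportion is an inference.

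**Conclusion.** The point holds and should be fixed. As written, the one named efficacy estimate counts a child treated for a low level at week 12 or 26 as a success if the week-52 level is above 30. For the single-dose question it can therefore be too favourable. Relative to the observed proportion sustained at every visit, it is equal or higher by k/30, or 3.3 points per child. This assumes a common threshold, complete levels and all 30 enrolled children dosed. The total effect is unknown, and the scenarios in the working are illustrations rather than predictions. Nor can the data show that a treated child's recovery was caused by the treatment.

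The differing success definitions are a real but smaller defect: the practical differences are the time frame, the upper limit of 100 and the boundary at exactly 30. The primary calcium endpoint and the sample size of 30 are unaffected.

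**What to change.** Change the analysis text only; no care rule changes.

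1. For the single-dose question, report the proportion meeting the threshold at week 52 with no earlier post-dose 25OHD below 30 and no step-wise or other high-dose vitamin D started. Count the others as not maintained. Show the as-measured week-52 proportion beside it, labelled as one dose followed by standard care, with the number treated and the number told to stop vitamin D supplements.
2. Report the week-12 proportion with its 95% confidence interval. It precedes any treatment triggered by a scheduled post-dose level.
3. Use one success definition in Sections 1, 3 and 9, stating whether exactly 30 and above 100 ng/mL count.
4. State the denominator as all dosed participants. Show missing levels both as not maintained and excluded, and keep retention as a separate result.
5. Record when added vitamin D starts. Section 4 already collects total cholecalciferol intake at each visit, but the calendar footnote limits the medication review to the "current daily maintenance dosage for vitamin D as previously prescribed"; the two should be aligned so that added treatment is captured.

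Cost: with the threshold unchanged, the headline 52-week rate is equal or lower, and there is slightly more analysis work. If the single definition adopted includes exactly 30, a child at that level would be added. No extra visits or blood draws are needed.

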Date: December 20, 2016

Principal Investigator: [name]

Application Number: IRB00081746 (IND # 128487 – IND Sponsor: [name])

Study Title: Safety, Efficacy, and Feasibility of High-dose Cholecalciferol in Pediatric Patients with Cystic Fibrosis

Principal Investigator: [name]

Application Number: IRB00081746 (IND # 128487 – IND Sponsor: [name])

Document: Protocol to accompany reported study results

NCT02613884

Date: December 20, 2016

Principal Investigator: [name]

Application Number: IRB00081746 (IND # 128487 – IND Sponsor: [name])

JHM IRB - eForm A – Protocol

Safety, Efficacy, and Feasibility of High-dose Cholecalciferol in Pediatric Patients with Cystic Fibrosis

1. Abstract

Children and adults with Cystic Fibrosis (CF) are at risk of developing a vitamin D deficiency or insufficiency, defined as a 25-hydroxyvitamin D (25OHD) serum blood level <30 ng/mL. Greater than 85% of people with CF have pancreatic insufficiency, which contributes to poor absorption of fat soluble vitamins and dietary fats. A 25OHD level greater than 30 ng/mL has been shown to provide improvements to markers of inflammation in adults with CF and is known to improve bone mineral density and prevent bone fractures in all populations, including CF. This study will assess the safety of a one-time high dose of cholecalciferol or vitamin D3 along with efficacy and feasibility of providing this therapy.

Children between the ages of 3 years and 18 years (inclusive), with a 25OHD level <30 ng/mL will be provided with a vitamin D3 supplement of 250,000 international units (IU) observed in our CF clinic. We hypothesize that this one-time, oral, high dose of vitamin D3 will safely and effectively raise the 25OHD level to above 30 ng/mL.

Safety will be monitored using a tiered safety protocol. Within the first tier, a serum calcium level and a serum phosphorus level will be measured at 1 week and 3 months following the dosage. This timing is appropriate as cholecalciferol has a half-life of 2-3 weeks and these timed levels would be at or near the middle of the 25-OHD range. A second tier safety evaluation will only be done if serum calcium levels or serum phosphorus levels are elevated. For this second tier, the participant will have a parathyroid hormone level measured (PTH) as well as a spot urine calcium to creatinine ratio.

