Research has displayed that the human body's response to vitamin D3 is biphasic, meaning it responds rapidly to low vitamin D3 doses and responds much slower to a larger vitamin D3 dose. Heaney et al. found that the low doses of vitamin D3 had a half-life of 20-30 days, but a high dose, such as 100,000 IU vitamin D3 had a half-life of 50 days (10). The authors hypothesized that perhaps at this higher dosage the vitamin D3 is being stored in fat and other body tissues and then slowly released; whereas the daily low doses of vitamin D3 provide an immediate increase or response that can sometimes be reflected in the blood sample.

In children and adults without malabsorption disorders, the current recommended range of daily vitamin D intake ranges from 400 IU per day for children as recommended by the American Academy of Pediatrics (11). Whereas the Institute of Medicine or IOM recommends a range of 600 IU to 4000 IU per day based on the age of the child. The IOM committee did increase its "upper level intake". That dose is 4,000 IU/day for adults, 3,000 IU/day for kids aged 4-8, 2,500 IU/day for kids aged 1-3, 1,500 IU/day for infants aged 6-12 months, and 1,000 IU/day for infants aged 0-6 months. The Endocrine Society for Patients at risk for vitamin D deficiency recommend a daily requirement of 400 IU-1000 IU for children depending on age and their upper level intake is 2000-4000 IU per day depending on age as well (12, 13). However, these recommendations are not for children with absorption disorders such as Cystic Fibrosis.

According to the National Institutes of Health, 25-OHD levels which are consistently greater than 200 ng/mL are "potentially toxic" (13). The IOM committee found no conclusive evidence that increased vitamin D levels confer increased health benefits, challenging the concept that "more is better". However, this was meant to be applied to healthy populations. A review of literature conducted in 2013 displayed that intoxication from vitamin D supplementation was rare in the pediatric setting. This same review also found that hypervitaminosis was "usually asymptomatic" and errors in formulation of the vitamin, manufacturing or prescription of the vitamin resulted in intoxication (13).

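### Section 9 estimates 25OHD efficacy only at study end (week 52), when step-wise treatment may have intervened; it needs a week-12 correction estimate and a counting rule

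*Combined protocol and SAP*

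**What the plan says.** Secondary objective 2 (Section 2) is to "Determine the efficacy of a single dose of oral vitamin D3 (250,000 IU) for the treatment of vitamin D insufficiency" in children with CF. The abstract's hypothesis is that one dose "will safely and effectively raise the 25OHD level to above 30 ng/mL". Neither gives a time point.

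Section 9 lists, among the feasibility and efficacy parameters, the "proportion of participants with serum 25OHD level >30 ng/mL at the end of the study"; these "will be calculated with the corresponding 95% confidence intervals". The term for study end is not defined, but the last visit in the Section 4 calendar is week 52 (±30 days). 25OHD is drawn at screening and at weeks 12, 26 and 52. The 12-week visit is the first after dosing: "from the initial study visit, participants will be required to have another 25OHD level measured". Section 9 names no estimate for the week-12 or week-26 values and no change from screening.

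Two other places bear on efficacy. The abstract treats levels within 30 to 100 ng/mL throughout the study as showing that the dose works. The end of Section 3 hypothesises that levels of 30 ng/mL or more will be maintained, and Section 11 hopes for an adequate level for up to 12 months.

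On other vitamin D, Section 4 keeps children on their prescribed CF vitamins and puts anyone below 30 ng/mL at any time after dosing onto the CF Foundation's step-wise treatment. Section 7 makes a need for outside high-dose vitamin D an off-treatment criterion but not an off-study one. Section 9 does not say how these children are counted.

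**The concern.** The plan asks two questions: does one dose correct a low level, and does the level stay corrected? Section 9 gives one number for both, taken at the point furthest from the dose. By then some children may have received further vitamin D precisely because the dose did not work or did not last. With a single arm, nothing in the design separates the dose from what followed it.

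At stake is the conclusion on secondary objective 2. The reported proportion could be low although the dose corrected most children at week 12, or high because step-wise treatment did the work.

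**Working it through.** **1. How the Section 9 rule classifies a child.** Possible courses under the Section 4 rules:

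| Week 12 | Then | Week 52 | Section 9 result | Corrected by the dose? | Maintained without step-wise treatment? |
|---|---|---|---|---|---|
| above 30 | no step-wise treatment | above 30 | success | yes | yes |
| above 30 | declines | below 30 | failure | yes | no |
| below 30 | step-wise treatment | above 30 | success | no | no |
| above 30 | below 30 at week 26, step-wise treatment | above 30 | success | yes | no |
| below 30 | step-wise treatment | below 30 | failure | no | no |

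Rows 2 and 3 are wrong for correction. Rows 3 and 4 are wrong for maintenance. This step uses no half-life.

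**2. How far the proportion can move (assumed rates).** Let q be the share above 30 at week 52 without step-wise treatment. Suppose all the rest are found below 30 at week 12 or 26 and treated, and a share s of them then exceeds 30. The reported proportion is q + (1 − q)s.

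| q | s = 0.2 | s = 0.5 | s = 0.8 |
|---|---|---|---|
| 0 | 20% | 50% | 80% |
| 0.2 | 36% | 60% | 84% |
| 0.4 | 52% | 70% | 88% |

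For example, 0.2 + 0.8 × 0.5 = 0.60. The documents give neither q nor s. Children first found low at week 52 could not be treated in time, so the shift would be smaller if many decline late.

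**3. What the protocol's half-lives imply.** The inputs are: "a high dose, such as 100,000 IU vitamin D3 had a half-life of 50 days" and "low doses of vitamin D3 had a half-life of 20-30 days" (both Section 3), and "cholecalciferol has a half-life of 2-3 weeks" (abstract). Assume simple exponential decline from day 0, so the fraction left is 0.5^(days / half-life). Nominal days are 84, 182 and 364.

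| Half-life | Week 12 | Week 26 | Week 52 |
|---|---|---|---|
| 50 days | 31.2% | 8.0% | 0.64% |
| 30 days | 14.4% | 1.5% | 0.02% |
| 20 days | 5.4% | 0.18% | under 0.01% |
| 21 days | 6.3% | 0.25% | 0.001% |
| 14 days | 1.6% | 0.01% | under 0.001% |

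At 50 days, week 52 is 364/50 = 7.28 half-lives (334/50 = 6.68 to 394/50 = 7.88 across the window). For an assumed initial rise of 20 to 80 ng/mL, that leaves about 0.1 to 0.5 ng/mL at week 52, against 6.2 to 25.0 ng/mL at week 12.

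**4. The week-12 window.** Days 54 to 114 correspond to 0.5^(54/50) = 47.3% and 0.5^(114/50) = 20.6% of the effect at 50 days. The remaining effect differs more than twofold across permitted visit dates.

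**5. Precision.** For the same number of children measured and the same proportion, the interval at week 12 is as wide as at week 52. With all 30 measured, exact 95% intervals are 47.2% to 82.7% for 20/30 and 61.4% to 92.3% for 24/30.

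The sample size of 30 is given without a target rate or interval width, so there is no plan figure to reproduce.

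**The case against.** Section 9 is not the only place that speaks of efficacy. The abstract's criterion covers all the post-dose draws, and Section 9's list is worded as not exhaustive. A reader might infer that the protocol never looks at earlier levels; it does not support that. What stands is that the abstract and Section 9 define efficacy differently and neither specifies a week-12 estimate.

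Maintenance is a stated hypothesis, and Section 11 looks to 12 months. A reader might infer that a week-52 level is irrelevant. It is not: it bears on durability. It is a poor sole measure of correction.

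The kinetic argument is the weaker of the two. A reader might infer that no effect of the dose could survive to week 52, or work back to the implausibly large initial rise that would be required. The documents do not support this. The 50 days is for 100,000 IU, and none is given for 250,000 IU or stated to be for serum 25OHD. Section 3 suggests that half-life lengthens with dose through storage and slow release, so 50 days is not shown to be an upper bound. If it were 100 days (an assumption), 0.5^(364/100) = 8% would remain. The abstract's 2 to 3 weeks would leave only 1.6% to 6.3% at week 12, which on kinetics alone would count against week 12 too.

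Finally, efficacy is secondary in an unpowered, single-arm study. The trial-design inputs listed under secondary objective 1(b) do not include 25OHD response, though Section 9's sample-size text speaks more generally of parameters for a later trial. The week-12 values are collected anyway and vitamin D intake is reviewed at those visits, so the information is not lost. That limits the harm; it does not supply the missing analysis.

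**Conclusion.** The point holds as a gap in the analysis plan. Followed as written, Section 9 reports a week-52 proportion that does not estimate whether one dose corrects insufficiency, because step-wise treatment follows any low level, CF vitamins continue, there is no comparator, and treated children have no counting rule. That conclusion rests on the documents' own rules and needs no pharmacokinetic assumption.

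Its size cannot be fixed from the documents. On the assumed rates, a 20% share above 30 without step-wise treatment could be reported as 36% to 84%. The half-life figures (about 0.6% left at week 52 against 31% at week 12) are supporting illustration only, resting on simple exponential decay and a figure for a different dose.

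Week 12 is preferable because it is the first scheduled post-dose draw and so precedes any step-wise treatment triggered by a study draw. It is still not a pure dose effect, since CF vitamins continue and there is no control arm. Reading study end as week 52 is an inference, though the natural one.

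**What to change.** In Section 9:

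- **Correction (secondary objective 2).** Make week 12 the estimate: the proportion reaching one stated threshold, with an exact 95% interval, and the mean change from screening with its SD and 95% interval. Plot or list values against actual days since dosing, because of the ±30-day window. State the denominator when a draw is missing.
- **Durability.** Report weeks 26 and 52 under this name. Count children who started step-wise or other high-dose vitamin D as not maintained by the single dose, or show results with and without them.
- **Consistency.** Align the abstract's criterion with Section 9 and use a single threshold. Above 30, at least 30, and 30 to 100 ng/mL all appear; a child at exactly 30 fails Section 9's rule yet is adequate by Section 3's definition. Define study end.

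The cost is analysis wording only: the draws and the medication review are already scheduled. The small downside is that the 12-month proportion becomes a durability result and may look less favourable.
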